8.1. Drugs (trade and generic, dosage, route of administration)

8.2. Devices

8.3. Biologics

Participants will be randomized 1:1 to eight weeks of BCAA or maltodextrin (PLA) supplementation. Participants will be instructed to consume either ~7-10 g of BCAAs (100 mg/kg body weight) (2:1:1 leucine:isoleucine:valine) or PLA powder.

8.4. Laboratory Tests

- a) **Laboratory Test:** We will collect plasma, serum, and whole blood for assessment of heart disease risk factors, complete blood count (CBC), comprehensive metabolic panel with liver function tests, lipid profile (e.g., triglycerides, lipoproteins, free fatty acids), glucose, insulin, systemic and cellular inflammation biomarkers, oxidative stress, antioxidant capacity, obesity-related factors (e.g., leptin and adiponectin), and amino acid metabolism.
- b) **Skeletal Muscle Biopsies and Analysis:** Vastus lateralis muscle biopsies will be obtained with a Bergstrom needle with local anesthesia by a credentialed clinician following a 12 hour fast. Muscle tissue will quantitate local inflammation and tryptophan metabolism markers. The samples will be placed in OCT for fiber typing or immediately placed in clamps cooled in liquid nitrogen. The de-identified frozen samples will be stored at -80°C in the Barshop Institute. Participants will be instructed to refrain from vigorous physical activity and to document their food intake during the 2 days before the biopsy and to repeat this diet before the post intervention biopsy. This procedure will not be performed if IV access cannot be

obtained, if the patient is anticoagulated for any reason and primary care physician does not feel it is safe for anticoagulant to be ceased for 1 week prior to the biopsy, if the patient does not tolerate a prior biopsy, or for any other concern as determined by the PI.

8.5. Imaging Procedures

Body composition: Whole body DEXA is performed to measure lean and fat body mass and to examine the effect of the interventions on body composition at baseline and after the intervention.

8.6. Other Research Procedures (e.g., other safety and efficacy assessments.)

Study Procedures:

- a) Questionnaires related to their health-related quality of life (PROMIS-57), fatigue assessment scale (FAS), Center for Epidemiologic Studies Depression Scale (CES-D), energy expenditure (Minnesota Leisure Time Physical Activity Questionnaire; MLTQ), activities of daily living, and dietary habits (short health eating index: sHEI) and sleep quality (Insomnia Severity Index: ISI). See Form M.
- b) Body composition: Minimum and maximum waist and hip circumference will be measured with a tape measure. Weight will be measured on a standard physician's scale.
- c) Energy Intake and Expenditure: *Energy intake* will be assessed through the Automated Self-Administered 24-Hour (ASA24®) Dietary Assessment Tool. Participants will be asked to self-administer 24-hour food recalls over a 3-5-day period and enter the information into the ASA24® web-based tool that enables multiple, automatically coded, self-administered 24-hour recalls. The latest release, ASA24-2016, also permits researchers to collect data using multi-day food records, also known as food diaries. Simultaneously, an activity monitor (Actigraph™) system will be used to monitor *total daily activity energy expenditure* (kcal/d). The Actigraph™ GT9x-BT accelerometers will be provided to participants upon meeting eligibility criteria. The monitors will be worn either on a belt around the hip or the wrist as he or she would a watch. Participants will wear the accelerometer for 5-7 days including the weekend. This measurement will be taken prior to randomization (Phase 3).
- d) Physical Fatigue:

Isometric Handgrip: Hand grip strength of both limbs will be assessed using a handheld dynamometer.

Strength: We will use a standardized 1-repetition maximum (1-RM) protocol that includes 4-6 trials with rest periods of the leg extension and chest press exercises. Participants also will be asked to perform the leg extension and chest press exercises at 60% 1-RM as many times as they can before fatigue.

Chair rise: The number of times that a participant can rise from a sitting to a standing position and to sit down again as quickly as they can in 30 seconds will be recorded. The time for the participants to rise five times from a sitting to a standing position and to sit down again also will be recorded.

Cardiopulmonary Exercise Test (CPET): A resting ECG will be performed prior to test. Open circuit spirometry will be performed during a cardiac exercise stress test using a customized protocol to evaluate the cardiopulmonary response (i.e., VO₂peak and ventilatory threshold) to strenuous exertion under clinical supervision and continuous vital signs and ECG monitoring according to the participant's tolerance, perceived exertion, and gait stability. These tests will be reviewed and cleared for participation by a research clinician. Participants breathe through a non-rebreather mask to collect expired air. A computer interfaced with gas analyzers continuously measures ventilation. Oxygen consumption, carbon dioxide production, and minute ventilation will be measured breath-by-breath using a metabolic cart.

Six-minute Walk Distance: We will measure the maximal distance the participants can walk during six minutes. Participants will be instructed to "cover as much distance as they can" over a flat surface demarcated by traffic cones while timed by a stopwatch.

- e) Frailty assessment: Frailty will be classified using the Fried phenotype criteria: 1) Self-reported unintentional weight loss of ≥ 10 pounds in the past year; 2) Self-reported exhaustion (CES-D); 3) Low energy expenditure using the Minnesota Leisure Time Physical Activity Questionnaire (MLTQ) to assess physical activity (duration and frequency); 4) Weakness measured via grip strength using a handheld dynamometer in the dominant hand; 5) and slowness on 10-foot walk at usual pace. These measures have been standardized in the SALSA study and will be used in this study as described (Espinoza, 2008). At the baseline, self-reported unintentional weight loss will be used as criteria for weight loss as stated above. A frailty score will be calculated as the number (0 – 5) of frailty characteristics present. Those with ≥ 3 of these 5 characteristics are categorized as frail; those with 1 or 2 are categorized as pre-frail, and those with none are categorized as non-frail (Fried et al., 2001).

8.7 Attach a Schedule of Activities (SOA) Excel File [Download the Template here: [Schedule of Activities](#)]

Check to indicate that the SOA Excel File is attached →

9.	Preparation/Handling/ Storage/Accountability of Investigational Drug, Biologic, or Device
	N/A - This study does not include any investigational products (e.g. drugs, devices or biologics)
	N/A - An Investigator Brochure is attached
	N/A - A Drug/Device Manual is attached
9.1. Acquisition and accountability State how the study intervention and control product will be provided to the investigator. Describe plans about how and by whom the study intervention will be distributed, including participation of a drug repository or pharmacy, and plans for disposal of expired or return of unused product.	

This study will utilize over-the-counter dietary supplement powders, neither of which require regulation by the FDA. Each will be purchased online and shipped to the Barshop Institute and stored in the clinical pharmacy.
 
The BCAA supplement we will utilize is manufactured and distributed by Naked Nutrition. 1 scoop (1Tbsp) contains 2500 mg of L-leucine, 1250 mg of L-isoleucine, and 1250 mg of L-valine and sunflower lecithin.
 
The maltodextrin placebo we will utilize is manufactured and distributed by nutricost. 1 scoop (15 g) contains 14 g of carbohydrate (maltodextrin).
 
Study staff will distribute the supplement to participants weekly and will ask for unused containers to be returned weekly. The distribution of supplement will be logged by study staff. Participants also will keep a log of supplement intake.
 
Expired and returned product will be discarded following pharmacy protocol.
	
9.2. Formulation, Appearance, Packaging, and Labeling Describe the formulation, appearance, packaging, and labeling of the study intervention and control product, as supplied. Information in this section can usually be obtained from the IB or the package insert, or device labeling. This section should include the name of the manufacturer of the study intervention and control product.	

Intervention blinded study staff wearing hair net, gloves and a facemask will weigh the required participant dose via nutrition food scale and place the daily dose in disposable polypropylene condiment containers and labeled with dates for daily intake.
	
9.3. Product Storage and Stability Describe storage and stability requirements (e.g., protection from light, temperature, humidity) for the study intervention and control product. For studies in which multi-dose vials are utilized, provide additional information regarding stability and expiration time after initial use (e.g., the seal is broken).	

The supplement will be stored per distributor recommendations (cool, dry place) in the Barshop clinical pharmacy.
	
9.4. Preparation Describe the preparation of the study intervention and control product, including any preparation required by study staff and/or study participants. Include thawing, diluting, mixing, and reconstitution/preparation instructions in this section. For devices, include any relevant assembly or use instructions.	

On exercise days, both powders will be dissolved in ~400 ml of a non-caloric drink of their choice (i.e., Crystal Light) in the clinical pharmacy by study staff. On non-exercise days, participants will be provided with the Crystal Light and provided written instruction to prepare the mixture.
	

10. Study Intervention Additional Details	
10.1. Measures to Minimize Bias: Randomization and Blinding This section should contain a description of randomization and blinding procedures (if applicable to the study design). It should include a description or a table that describes how study participants will be assigned to study groups, without being so specific that blinding or randomization might be compromised. Plans for the maintenance of trial randomization codes and appropriate blinding for the study should be discussed. The timing and procedures for planned and unplanned breaking of randomization codes should be included. Include a statement regarding when unblinding may occur and who may unblind. Provide the criteria for breaking the study blind or participant code. Discuss the circumstances in which the blind would be broken for an individual or for all participants (e.g., for serious adverse events (SAEs)). Indicate to whom the intentional and unintentional breaking of the blind should be reported.	

Randomization codes will be created at random and kept electronically by a study team member not directly involved with participants (i.e., statistician). We anticipate that blinding will only be broken prior to completion of the study if requested by the DSMB due to safety concerns. Unblinding prior to study completion will be reported to the IRB, study sponsor and DSMB.
 
Randomization code: a random number generator will be used utilizing numbers 1 and 2 where 1=placebo group 2= BCCA group
	
10.2. Study Intervention Compliance Define how adherence to the protocol (e.g., administration of study intervention, use of device,) will be assessed, and verified (if applicable, e.g., plasma assays, electronic monitoring devices, daily diaries).	

Compliance will be assessed weekly via intake logs and return of unused supplement.
	

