Tryptophan Metabolism as a Mechanism Influencing Fatigue During Exercise: Evidence in animal models suggests that reductions in physical fatigue often observed with exercise training are mediated by skeletal muscle peroxisome proliferator-activated receptor γ co-activator 1 α (**PGC-1 α**), inducing a shift of kynurenine to kynurenic acid ((Agudelo et al., 2014; Agudelo et al., 2019). This is catalyzed by kynurenine aminotransferase (**KAT**) enzymes, which prevents oxidative metabolism of kynurenine and also its entry into the CNS, which may have an influence on mental fatigue. We have shown that reductions in skeletal muscle inflammation are associated with reductions in mental and physical fatigue following exercise training (Serra et al., 2018); however, a recent study in older adults also found that exercise training significantly increased skeletal muscle PGC-1 α gene expression and KAT isoforms nearly two-fold (Allison et al., 2019). These data suggest that the tryptophan metabolism pathway may play an integral role in regulating mental and physical fatigue with exercise.

Though we have shown that exercise training can reduce the incidence of moderate-to-severe mental and physical fatigue by 30-60%, we also find that 82% of subjects continued to report mild fatigue after the intervention (Serra et al., 2018).

Further, our preliminary data suggest that when participating in exercise training, older adults tend to reduce their free-living activity by ~20% and report acute fatigue follow exercise as a contributing factor. Therefore, identifying methods to prevent acute fatigue during exercise and maximize the fatigue-reducing abilities of chronic exercise training in older adults is needed.

Potential of Branched-Chain Amino Acid Supplementation to Reduce Mental and Physical Fatigue When Combined Exercise: Exhaustive exercise results in the branched-chain amino acids (**BCAA**: leucine, isoleucine and valine) being taken up by the muscle, leading to reductions in the plasma concentration. When consumed as a nutritional supplement, BCAAs may improve circulating concentration of physical fatigue substances (lactate, ammonia and 5-hydroxytryptamine), energy metabolites (glucose and free fatty acids) and muscle soreness substances (lactate dehydrogenase

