Screening: Eligible volunteers will have the study explained and provide informed consent according to the guidelines of the UT Health San Antonio IRB. Participants will be asked to supply the name and contact information of their primary care provider during the consent/screening phase. An in-clinic evaluation consisting of medical history and physical exam (including EKG) will be conducted by a research clinician. Information on demographics and family medical history will be recorded. A fasting blood profile for lipids, liver, renal and hematological function will be drawn. We will draw approximately 30 ml of blood (about 2 tablespoons) during screening (*Phase 1*). Although we do not expect a problem with the collection of blood samples, should a problem arise, such as clotting or insufficient sample for analysis, we may draw additional blood, not exceeding 50 ml (10 teaspoons) throughout any study visit. Height and weight will be measured using a standard physician's scale. Seated blood pressures will be measured. Questionnaires to screen for depression and cognitive impairment will be administered to determine eligibility.

Enrollment: Participants will be enrolled if they provide informed consent and pass all required screening assessments.

Baseline Research Testing (Phase 2): Data for primary and secondary outcomes will be collected using standardized protocols and trained staff. All baseline testing will be conducted at the Barshop Institute over approximately 3-4 visits during approximately 2-4 week period. These tests are described in detail below.

Randomization (Phase 3): Assigned (1:1 randomization) to either EX+PLA or EX+BCAA. After randomization, vital signs and blood will be drawn before (following a 12 hour fast) and acutely (3-5 min) after completing a 400 m walk test. After the fasting blood draw, participants will receive (blinded) either ~7-10 g of BCAAs (100 mg/kg) or maltodextrin (depending upon group allocation) 30 min prior to beginning this test. Heart rate and ratings of perceived exertion will be collected throughout the 400 m walk test. Participants will be instructed to document their food intake on Food Record form during the 2 days before the 400 m walk test and to repeat this diet before the post intervention test.

Exercise + Placebo or Exercise + BCAA (Phase 4):

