Exercise: The 3x/wk for eight weeks exercise protocol is designed to provide a high-volume, moderate-intensity whole body training stimulus for all participants. The sessions will occur at the Barshop Institute and be led by an exercise physiologist.

Aerobic exercise training will start conservatively with a goal of 30 minutes total duration at 40-50% maximal heart rate reserve (HRR) determined according to the formula of Karvonen: Training HR = % (HRmax - HRrest) + HRrest. HRmax is defined as peak heart rate based during a peak Cardiopulmonary Exercise Test (described above). Treadmill exercise is advanced weekly, as tolerated to an intensity of 75-85% HRR for 30 minutes. Additionally, participants will perform resistance exercise consisting of 15 repetitions for two sets and to exhaustion on the third set for five major muscle groups: chest press, knee extension, leg curl, row, and bicep curl. Resistance is gradually increased to account for strength gains when participants are able to complete 20 repetitions on the third set.

BCAA or Placebo: Participants will be randomized 1:1 to eight weeks of BCAA or maltodextrin (PLA) supplementation. Participants will be instructed to consume either ~7-10 g of BCAAs (100 mg/kg body weight) (2:1:1 leucine:isoleucine:valine) or PLA powder. In the Barshop Institute pharmacy, intervention blinded study staff wearing hair net, gloves and a facemask will weigh the required participant dose via nutrition food scale and place the daily dose in disposable condiment containers and labeled with dates for daily intake. Powders will be distributed in a double-blind fashion, identical in color, and dissolved in water or a non-calorie drink of their choice (i.e., Crystal Light). On non-exercise days, participants will be instructed to take the supplement between 9 - 10 am each morning and to log each intake in a provided spreadsheet. Powders to be consumed on non-exercise days will be pre-packaged containers and provided to participants on a weekly basis. On exercise days, the supplement will be consumed immediately after finishing exercise training. Supplement containers also will be returned every two weeks to track compliance. Assessment of side effects will occur at every exercise session.

Post Intervention Testing (Phase 5): Participants will repeat tests outlined in Phase 2 and the submaximal exercise test outlined in Phase 3.

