12.4. Statistical Analyses

Include analysis of primary efficacy endpoints, secondary endpoints, safety analyses, and any planned interim analyses

In collaboration with RC3 (Trial Design and Integrative Informatics Core), two separate independent sample t-tests will be used for each outcome measure: one to compare change before and after acute exercise (during the 400 m walk) between the two groups and one to compare change before and after chronic (8-week) exercise training between the two groups. This will determine the significance of our primary outcomes (fatigue and tryptophan metabolism) change over time. All statistical tests will be 2-sided and unadjusted for multiple comparisons. We are eschewing the mixed model analysis of variance (ANOVA) to account for the time effect. The repeated measures ANOVA would be testing more effects than we are exploring here, and the study is not powered for this advanced analysis.

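### The activity monitor may be worn on the hip or the wrist with no rule fixing or recording the site, so activity energy expenditure may not be comparable across participants or visits.

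*Combined protocol and SAP*

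**What the plan says.** Section 8.6 c) introduces an accelerometer that "will be used to monitor *total daily activity energy expenditure* (kcal/d"). On placement it says: "The monitors will be worn either on a belt around the hip or the wrist as he or she would a watch". On duration: "Participants will wear the accelerometer for 5-7 days including the weekend". On timing: "This measurement will be taken prior to randomization (Phase 3"). No scoring algorithm, epoch or site-recording step is given.

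Section 7, under Post Intervention Testing (Phase 5), gives a general rule: "Participants will repeat tests outlined in Phase 2 and the submaximal exercise test outlined in Phase 3". Under Baseline Research Testing (Phase 2), the same section identifies the Phase 2 tests only by pointing forward: "These tests are described in detail below". The monitor is among the procedures that follow, so a Phase 5 repeat can be inferred, but section 8.6 c) does not state one. The Schedule of Activities named in section 8.7 is a separate file and is not part of the text reviewed here.

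Section 12.4 applies independent-sample t-tests to each outcome measure, including "one to compare change before and after chronic (8-week) exercise training between the two groups". It names fatigue and tryptophan metabolism as the primary outcomes. Activity energy expenditure is not named.

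**The concern.** If the two sites give different readings for the same activity, a kcal/d value depends partly on where the monitor sat. There are two routes to harm. Between participants, a mixture of sites widens the spread of baseline values. Within a participant, a move from one site to the other between Phase 2 and Phase 5 puts a change of site into the change score.

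The plan is more careful elsewhere. Section 7 promises standardized collection of outcome data, section 8.6 e) fixes the dominant hand for the frailty grip test, and section 8.4 b) asks for the same diet before both biopsies. Wear site has no such rule.

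The measure is relevant to the trial's reasoning. Section 2 reports that during training "older adults tend to reduce their free-living activity by ~20" per cent, with acute fatigue as a contributing factor. Among the listed procedures the accelerometer is the only device-based record of free-living activity; the Minnesota questionnaire in 8.6 a) is self-report. With 24 planned completers there is little room for avoidable noise. If the site is not recorded, the analysis cannot adjust for it afterwards.

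**Working it through.** **What can be reproduced.** The plan states no effect, SD, power or site difference for activity energy expenditure, so there is no figure to reproduce. What follows is illustration. Only the 12 completers per group (section 12.2) and the two-sided 5% t-test on change (sections 12.2 and 12.4) come from the documents.

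**1. Nobody switches site.** Let the true change be D. If the site difference is additive, it cancels in D. If it is proportional, it cancels in log change, but not in raw kcal/d: at a 20% site difference the same D is recorded as D at one site and 1.2 × D at the other. Section 12.4 does not say which scale is used.

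**2. Some switch, log scale.** Assumptions: SD of true log change s = 0.2 to 0.3; share switching p = 0 to 0.5, balanced in direction; proportional site difference b = 0.2 or 0.5.

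Inflation of the SD = √(s² + p × [ln(1 + b)]²) / s

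- p = 0: ratio 1.00 for any b.
- b = 0.2, [ln 1.2]² = 0.0332:
  - s = 0.3, p = 0.25: √(0.0900 + 0.0083) / 0.3 = 1.05
  - s = 0.2, p = 0.50: √(0.0400 + 0.0166) / 0.2 = 1.19
- b = 0.5, [ln 1.5]² = 0.1644:
  - s = 0.3, p = 0.25: √(0.0900 + 0.0411) / 0.3 = 1.21
  - s = 0.2, p = 0.50: √(0.0400 + 0.0822) / 0.2 = 1.75

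**3. Some switch, in SD units, with power.** Let the additive site offset be b SDs of true change, and let a fraction q switch in each direction. The SD ratio is √(1 + 2q × b²). Power is for a two-sided 5% two-sample t-test, 12 per group, and an assumed true difference of 1 SD.

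| Offset b | q | SD ratio | Power |
|---|---|---|---|
| any | 0 | 1.00 | 0.65 |
| 0.5 | 0.10 to 0.25 | 1.03 to 1.06 | 0.63 to 0.60 |
| 1 | 0.10 to 0.25 | 1.10 to 1.22 | 0.57 to 0.48 |
| 2 | 0.10 to 0.25 | 1.34 to 1.73 | 0.42 to 0.27 |

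**4. Baseline only, sites mixed 50:50 across participants.** With b now in between-person SDs, the SD ratio is √(1 + b²/4): 1.03, 1.12 and 1.41 for b = 0.5, 1 and 2.

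**5. Chance imbalance.** If each participant's site is random 50:50, the numbers X and Y on one site in two arms of 12 are independent binomials, and X − Y + 12 is binomial with n = 24 and probability 0.5. The chance that the arms differ by three or more participants is about 0.31. A difference of exactly three moves the difference in arm baseline means by 3/12 × b = 0.25b between-person SDs, with no preferred direction.

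**The case against.** The strongest reply is that the text is permissive and describes neither mixing nor switching. It is compatible with one site for the whole study, with one site kept by each participant, or with site-specific scoring. That stands: the point is that comparability is not assured, not that it has been lost.

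Second, section 8.6 c) times the measurement only before randomization, whereas section 8.5 says outright that DEXA is done at both time points. If the monitor is worn only at baseline, the switching calculations (steps 2 and 3) do not apply. That also stands as a condition. The repeat rule in section 7 points the other way, so the two need reconciling, and the between-participant problem in step 4 remains in either case.

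Third, nothing in the documents supports a 25-50% switching rate, and the size of any hip-to-wrist difference is not given. Both are assumptions. At zero switching the log-scale inflation is nil.

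A reader might go further and infer that unequal site use would bias the comparison of arms. The documents do not support this. Allocation is random, participants and intervention staff are blinded, and nothing ties site to arm, so chance imbalance is random error. A reader might also take the figure of about 20% in section 2 as the effect the trial must detect. It is preliminary background on activity falling during training, not a planned difference between arms.

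**Conclusion.** The concern holds in a limited form. The plan allows two wear sites for one kcal/d measure, and nothing in the available text fixes, holds constant or records the site. The data may therefore mix sites across participants and, if the monitor is repeated in Phase 5, within them. It would go beyond the text to say that the values are in fact on two scales.

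The expected harm is lost precision and chance imbalance. Its size is unknown. The illustrations run from no inflation of the SD of log change (no switching, proportional site difference) to 75% (half switching, 50% site difference, s = 0.2). If the two sites gave the same reading, there would be no effect at all. The measure is supporting: fatigue, tryptophan metabolism and the sample size are unaffected. The change is worth making because it costs almost nothing now and an unrecorded site cannot be corrected in the analysis.

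**What to change.** 1. In section 8.6 c), replace the hip-or-wrist alternative with one named wear site, one scoring algorithm and one epoch for all participants at every measurement.
2. Add that a participant who cannot use that site keeps the same alternative throughout, and that the site is recorded at each measurement.
3. Reconcile the timing sentence in 8.6 c) with the Phase 5 rule in section 7. State whether the monitor is worn again after the intervention, and make the Schedule of Activities agree.

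The cost is two or three sentences and one case-report field. Items 1 and 2 need no extra visit or equipment. Item 3 only settles what is already implied.
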